### 7.3.1 Primary endpoint analyses

In the primary analysis, the two-sided hypothesis as given in [Section 7.2](#) will be tested based on adjusted mean change from baseline in LVEDVI, as listed in [Section 5.1.1](#), using a restricted maximum likelihood (REML)-based MMRM. This model will include treatment and period as fixed effects, patient as a random effect and baseline as covariate. Unstructured covariance structure will be used for within patient variation. If convergence is not achieved, the compound symmetry covariance structure will be used. The SAS procedure MIXED will be used involving the restricted maximum likelihood estimation and the Kenward-Roger approximation for denominator degrees of freedom. This approach is described in [[R10-4391](#)]. Adjusted mean values as well as treatment contrasts will be presented together with the 95% confidence intervals (CI) and p-values.

#### Baseline

The baseline is defined as the (pre-dose) measurement in, the LVEDVI performed in a week prior to Visit 2 (or prior to dosing on the Visit 2).

### 7.3.2 Secondary endpoint analyses

The MMRM model described for the primary analysis will be performed for secondary endpoints as listed in [Section 5.1.2](#). Adjusted mean values as well as treatment contrasts will be presented together with the 95% CI. All calculated p-values should be considered descriptive for the analysis of the secondary endpoints.

### 7.3.4 Safety analyses

Adverse events will be coded using the Medical Dictionary for Regulatory Activities (MedDRA) coding dictionary. Standard BI summary tables and listings will be produced. All adverse events with an onset between start of treatment and end of the residual effect period (REP), a period of 21 days after the last dose of trial medication, will be considered 'treatment-emergent'. Adverse events that start before first drug intake and deteriorate under treatment will also be considered as 'treatment-emergent'. Adverse events with an onset from the start of treatment to Visit 3 will be assigned to the first treatment, and adverse events with an onset on a day after Visit 3 to the end of REP to the second treatment.

All treated patients will be included in the safety analysis. In general, safety analyses will be descriptive in nature and will be based on BI standards. No hypothesis testing is planned.

Frequency, severity, and causal relationship of adverse events will be tabulated by system organ class and preferred term after coding according to the current version of the MedDRA.

Blood pressure and pulse rate measured in conjunction with PFT testing will be presented for each treatment using descriptive statistics.

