PFT	Pulmonary function testing
PRN	pro re nata (as needed)
PWA	Pulse Wave Analysis
qd	quaque die (once a day)
REML	Restricted Maximum Likelihood
REP	Residual effect period, after the last dose of medication with measureable drug levels or pharmacodynamic effects still likely to be present
RV	right ventricular
RVol	Residual Volume

SAE	Serious Adverse Event
SGOT	Serum glutamic-oxaloacetic transaminase
SGPT	Serum glutamic-pyruvic transaminase
SGRQ	St. George's Respiratory Questionnaire
SOP	Standard operating procedures
SmPC	Summary of Product Characteristics
STORM	storage conditions for trial medication
SUSAR	Suspected Unexpected Serious Adverse Reaction
SVI	Stroke volume index
TCM	Trial Clinical Monitor
TDI	Transitional dyspnoea index
TLC	Total Lung Capacity
TMF	Trial Master File
TSAP	Trial Statistical Analysis Plan
UK	United Kingdom
US	United States

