### 3. DESCRIPTION OF DESIGN AND TRIAL POPULATION

#### 3.1 OVERALL TRIAL DESIGN AND PLAN

This is an exploratory, randomised, double-blind, double-dummy, active-controlled, two-period complete cross-over study to investigate the effect of 6 weeks treatment of orally inhaled tiotropium + olodaterol FDC (5 µg / 5 µg) (delivered by the Respimat® Inhaler) compared with fluticasone propionate + salmeterol (1000 µg / 100 µg) (delivered by the Accuhaler® Inhaler) on left ventricular function and arterial stiffness in patients with COPD.

The trial consists of a run-in period, two 6-week treatment periods with no washout in between the treatments and a follow-up period.

[figure not shown]

Figure 3.1:1. Overview of the trial design

After signing Informed Consent and completing an initial screening visit (Visit 1), patients will enter a 3 to 4-week run-in period to reach their baseline level of diastolic heart function prior to changes under treatment. In a week prior to randomisation, patients will conduct an assessment of heart (left ventricular) function with CMR examination.

Patients who meet all the inclusion criteria and none of the exclusion criteria will be randomised at Visit 2 into the first of 2 x 6-week double-blind, cross-over treatment portion of the study, in which they will receive one of two treatments with the treatment codes as follows:

- A. tiotropium + olodaterol (5 µg / 5 µg) FDC inhalation solution, delivered once daily via the Respimat®
- B. fluticasone propionate + salmeterol (1000 µg / 100 µg) dry powder for inhalation, delivered twice daily via the Accuhaler®

The randomised treatment sequences are AB and BA. An interactive voice/web response

system named Interactive Response Technology (IRT) will be used for randomisation to a treatment sequence in this trial and for appropriate re-supply of medication to patients.

Patients will be evaluated for an additional 21 days following completion of the last 6-week randomised treatment period, or in case of discontinuation, after the final dose of study medication. In this follow-up period patients may return to their medication prescribed prior to participating in the study. The patient's trial participation will be concluded with the follow-up visit 21 days after the end of treatment. For visit details please refer to [Section 6.2](#).

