Because the duration of each treatment is 6 weeks, the pharmacodynamic steady state on lung function and hyperinflation would sufficiently be reached without the washout between the treatment periods. It is expected that in the treatment change from tiotropium + olodaterol to fluticasone propionate + salmeterol (AB sequence) there will be some additional bronchodilatory effect of tiotropium, lasting at most a couple of days that will rapidly and completely disappear when pharmacodynamic steady state of both treatments in the second treatment periods will be reached. No measurements are planned in this period but only at the end of each treatment period.

Since patients will be randomised to a treatment sequence AB or BA that includes either both a long-acting  $\beta_2$ -agonist (olodaterol) and a long-acting anti-cholinergic (tiotropium) or an intermediate acting  $\beta_2$ -agonist (salmeterol) and inhaled corticosteroid (fluticasone), it is necessary to restrict the use of long-acting  $\beta_2$ -agonists (e.g. salmeterol, formoterol, indacaterol), anti-cholinergics (e.g. tiotropium, ipratropium) and inhaled corticosteroids (iCS) during the entire treatment phase. Short-acting  $\beta_2$ -agonist medication (salbutamol / albuterol) and /or short acting anticholinergic (ipratropium; primarily to patients who are required to washout LAMAs during run-in periods) will be provided to patients for rescue use (as needed, PRN) in run-in and treatment periods with short washout of short-acting bronchodilators prior to CMR and PFT assessments.

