### 5.3.6.2 Adverse event collection and reporting

#### **AE Collection**

The Investigator shall maintain and keep detailed records of all AEs in their patient files.

The following must be collected and documented on the appropriate CRF(s) by the Investigator:

- From signing the informed consent onwards through the Residual Effect Period (REP), until individual patient's end of trial:
  - All AEs (serious and non-serious).
- After the individual patient's end of trial:
  - The Investigator does not need to actively monitor the patient for AEs but should only report relevant SAEs and relevant AESIs of which the Investigator may become aware of.

[figure not shown]

Figure 5.3.6.2: 1 AE collection in 1237.36

The REP is defined as 21 days after the last trial medication application. All AEs which occurred through the treatment phase and throughout the REP will be considered as on treatment please see [Section 7.3.4](#). Events which occurred after the REP will be considered as post treatment events.

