6. GENERAL ANALYSIS DEFINITIONS

6.1 TREATMENT(S)

The doses to be administered are described in Section 4 of the CTP.

This is a crossover trial consisting of a one to three-week run-in period followed by two six-week treatment periods and a three-week post-treatment period. The day after the follow-up visit will be considered the start of the post-study period in case there are any subsequent AE data we become aware of. In this study, there will be no washout between treatment periods.

In general, the first period will be considered last until 12 hours after the last intake of medication assigned for the first period, then the second period will start

For the main safety analysis, data occurring during the treatment periods and within 21 days of stop of study drug for that period will be assigned to the respective treatment for that period. Data occurring before the first drug intake date is assigned to "screening". If the next treatment period starts within 21 days of the end of the last period, data after the start of treatment for the next period will be assigned to the treatment for that period. In this trial, next treatment will be started after end of treatment of first period as soon as possible because there is no washout period planned. The last day of the first period is the day of the last intake of medication for the first period. AEs occurring at the last day of the first period will be assigned to the first period even if the medication of the evening dose already belongs to the second period. Data more than 21 days after drug stop date for a period but before the start of the next period will be assigned to washout. Data more than 21 days after the end of the last treatment period and up to and including the date of the study termination will be assigned to follow-up.

Any cases of patient being treated with the wrong study medication will be identified and summarised as an important protocol violation (PV).

- If a patient was treated with a treatment sequence different from the randomised treatment sequence throughout the on-treatment period, i.e., a patient was treated with incorrect study medication during every treatment period, this patient will be included in the treated set and will be analysed as treated for both efficacy and safety analyses, including patient disposition. Such a case will be reported as an important PV and this patient will be excluded from the per-protocol set (PPS).

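### Adverse events in the first 21 days after the switch are credited only to the second treatment, although they also fall in the first treatment's residual effect period, which can dilute differences in events with a residual effect

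*Protocol*

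**What the plan says.** Protocol 3.1 describes "two 6-week treatment periods with no washout in between the treatments". On the residual effect period, Protocol 5.3.6.2 states: "The REP is defined as 21 days after the last trial medication application". It treats events in that time as on treatment. The abbreviation list describes the REP as a period "after the last dose of medication with measureable drug levels or pharmacodynamic effects still likely to be present".

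Protocol 7.3.4 credits events up to Visit 3 to the first treatment, and "adverse events with an onset on a day after Visit 3 to the end of REP to the second treatment". SAP 6.1 first gives every period its own window, so that data "within 21 days of stop of study drug for that period will be assigned to the respective treatment for that period". It then overrides that window when the next period begins within it: "data after the start of treatment for the next period will be assigned to the treatment for that period". It notes that no washout is planned, and it settles the switch day itself in favour of the first treatment.

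Protocol 3.2 discusses the switch from tiotropium + olodaterol to fluticasone propionate + salmeterol and expects "some additional bronchodilatory effect of tiotropium, lasting at most a couple of days". Safety analyses are descriptive; Protocol 7.3.4 says "No hypothesis testing is planned". SAP 7.8.1 counts subjects with events, not events. It describes no flag, by-sequence display or supportive table for events early in period 2.

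**The concern.** The same drugs are handled differently in the two periods. After period 2, the 21 days following the last dose count towards the drug just stopped. After period 1, they count towards the drug just started, from the day after Visit 3 onwards. If a type of event can still arise from the first drug in those days, it appears in the other drug's column. This happens in both sequences and in the same direction, so equal allocation balances observation time but does not remove the misattribution.

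At stake is how the by-treatment adverse event tables are read, since they are the planned safety comparison. With about 74 patients, a few moved events can change the impression. The planned tables would not show how many events lie in the overlap.

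**Working it through.** The plan gives no figure of its own on this point, so there is none to reproduce.

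**Inputs.** Two periods of 42 days with no washout (Protocol 3.1); a 21-day REP (Protocol 5.3.6.2); 1:1 allocation to AB or BA (Protocol 4.1.4.1). Nominal Visit 3 is day 43 and Visit 4 is day 85 (flow chart).

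**Overlap.** The switch day belongs to the first treatment. Days 44 to 85 are the 42 days of period 2, and days 44 to 64 are the first treatment's REP.
- Share of period 2 on treatment: 21/42 = 50%.
- Share of period 2 including its own 21-day tail: 21/63 = 33%.
- Share of each treatment's on-treatment time over both sequences: 21/84 = 25%.
- The same with the tail counted: 21/105 = 20%.

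**Dilution.** Let drugs A and B have excess event rates a and b per day. Assume that each drug's excess continues after the switch for the equivalent of L full-rate days. Pooling the two sequences over on-treatment time:
- column A shows a + bL/84;
- column B shows b + aL/84;
- the difference is (a − b)(1 − L/84).

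The errors from AB and BA therefore add up and do not cancel. If the 21-day tail after period 2 is counted at the full rate, 84 becomes 105.

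| Assumed duration | L | Loss, L/84 | Loss, L/105 |
|---|---|---|---|
| 2 days, full effect | 2 | 2.4% | 1.9% |
| 7 days, full effect | 7 | 8.3% | 6.7% |
| Linear decay over 21 days | 10.5 | 12.5% | 10.0% |
| 21 days, full effect | 21 | 25.0% | 20.0% |

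The last column treats the tail after period 2 as running at the full rate, which is exact only for full persistence. If that tail decays in the same way, the loss is L/(84 + L). For linear decay this is 10.5/94.5 = 11.1%, inside the 10-12.5% range. For 2 days it is 2/86 = 2.3%.

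**As a rate ratio, under full 21-day persistence.** Take a background rate of 1 under both drugs, with an excess for A only.
- A true ratio of 2.0 appears as 2/1.25 = 1.60 on treatment, or 2/1.2 = 1.67 with the tail.
- A true ratio of 1.5 appears as 1.5/1.125 = 1.33, or 1.5/1.1 = 1.36.

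**Limit of the model.** These are rates per day at risk. SAP 7.8.1 tabulates subjects with at least one event, and the documents give no event rates from which to convert.

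**The case against.** The rule is deliberate, prespecified and the same in both documents. SAP 6.1 foresees a new period starting inside the 21 days. Without a washout, some single-attribution rule is needed to avoid counting an event twice. All of this stands, and the main rule should stay.

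The protocol also considers carry-over, and the only duration it states is a couple of days, at which the loss is about 2%. That is fair, but the statement covers tiotropium bronchodilation in sequence AB. It does not cover the other sequence or adverse events in general, and the documents do not reconcile it with a 21-day REP.

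Safety is descriptive, so no error rate or primary conclusion depends on this. That also stands. The SAP refers to internal guidance and standard listings that are not in the documents, so whether a listing already shows onset by period cannot be judged.

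Two stronger readings are tempting.

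- A reader might infer that every safety difference is blurred. The documents do not support this: only event types with a residual effect are diluted, and nothing says that event risk stays raised for 21 days. The phrase about effects being likely to persist is a general definition in the abbreviation list. Nor do the documents identify a particular event, such as one from the inhaled corticosteroid, as carrying over.
- A reader might infer a loss of 20% for linear decay and 33% for full persistence. These follow from counting excess events per course: 10.5/(42 + 10.5) = 20% and 21/(42 + 21) = 33%. The reference there is a complete 63-day count after both periods, which single attribution without washout cannot give. The SAP does not tabulate events per course.

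**Conclusion.** The point holds as a minor one. Both documents credit events after the Visit 3 day only to the second treatment, while the first treatment's REP, as the plan defines it, runs over half of period 2. For event types with a residual effect, the by-treatment rates are drawn together.

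The size depends on a duration that the documents do not give. The range is about 2% of the rate difference for a couple of days, 10-12.5% for linear decay over 21 days, and 20-25% for full persistence. It assumes 42-day periods, equal sequences and an additive excess rate. The difference is diluted, not erased.

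**What to change.** Keep the main attribution rule. In SAP 6.1, state that events with onset in the first 21 days of period 2 also fall in the REP of the first treatment. In SAP 7.8.1, add text such as: *Treatment-emergent AEs and SAEs with onset in the first 21 days of period 2 will be flagged and shown separately by sequence. The by-treatment AE summary will be repeated without them as a supportive table.*

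The flag uses dates already collected. Dosing, visits, data collection and the primary analysis do not change. The cost is a little more output. In the repeat table each treatment keeps 63 of 84 on-treatment days (84 of 105 with the tail), so it has fewer events. It also removes early reactions to the newly started drug and could hide a real difference of that kind. It must be read beside the main table, not in place of it.

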### **7.3.5 Pharmacokinetic analyses**

No pharmacokinetic analysis is planned.

### **7.4 INTERIM ANALYSES**

No interim analysis is planned.

### **7.5 HANDLING OF MISSING DATA**

In general, missing data at a given visit will be imputed by the available data from the patient at that visit and completely missing visits will be handled through the statistical model.

Additional details on the imputation of missing data will be specified in the TSAP prior to unblinding.

### **7.6 RANDOMISATION**

Approximately 74 patients will be randomised in blocks to double-blind treatment sequence so that approximately equal numbers of patients will be randomised to each treatment sequence. BI will arrange for the randomization and the packaging and labelling of trial medication. The randomization list will be generated using a validated system, which involves a pseudo-random number generator so that the resulting treatment will be both reproducible and non-predictable. The block size will be documented in the CTR. Access to the codes will be controlled and documented.

### **7.7 DETERMINATION OF SAMPLE SIZE**

This is an exploratory trial and only limited data exist about LVEDVI. A cross-over study in COPD patients evaluated the effect of fluticasone furoate and vilanterol versus placebo on mean change from baseline in LVEDVI [[R16-3512](#)]. The mean difference was 3.63 mL/m^2 with a standard deviation of approximately 7.3 mL/m^2. Assuming a 2-sided alpha of 5% and a within-patient standard deviation of 7.5 mL /m^2, a sample size of approximately 74 patients would have 80% to 90% power to reject the null hypothesis if the true treatment difference is 2.5 to 3.0 mL/m^2. If the SD is 20% larger (9.0 mL /m^2), then the power would still be 80% for a treatment difference of 3.0 mL/m^2. This results in a sample size of 74 patients.

Table 7.7: 1                      Sample size for 80% and 90% power, 2-sided alpha= 0.05

Power	Difference [ml/m  ]	SD	Sample Size
80%	3.0	7.5	52
90%	3.0	7.5	68
80%	3.0	9.0	74
90%	3.0	9.0	98
80%	2.5	7.5	74
90%	2.5	7.5	98

Calculations were performed using nQuery Advisor® 7.0 statistical package by Statistical Solutions Ltd.

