### 3.3 SELECTION OF TRIAL POPULATION

A sufficient number of patients will be enrolled (sign informed consent) to ensure that approximately 74 patients of either sex, 40 to 75 years old, with a diagnosis of COPD are randomised into the study. All patients are expected to be randomised within eight months of overall trial initiation (i.e. initiation of the first site), which requires a minimum enrollment of 2 patients per month at each site.

Enrolment will be competitive and conducted at approximately 10 study sites. Additional

sites may be initiated and 'non-productive' sites may be closed to ensure sponsor's timelines. It is anticipated that each site will enroll an average of approximately 8 patients.

Patients will be required to perform lung function testing with body plethysmography on several occasions in the study. They will also be performing CMR 3 times in the trial. Each examination is estimated to last up to one hour and will be conducted as a non-contrast and non-stress MRI procedure. For this reason any patients with general contraindications to magnetic resonance procedure will be excluded from participation.

A log of all patients enrolled into the trial (i.e. who have signed informed consent) will be maintained in the ISF at the investigational site irrespective of whether they have been treated with investigational drug or not.

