### 7.3 PLANNED ANALYSES

The efficacy analysis will be performed in all randomised patients who were documented to have received any dose of trial medication and who have both baseline and any evaluable post-baseline measurement for the primary endpoint or secondary endpoints. This set will be called Full Analysis Set (FAS).

The data from patients who have had an exacerbation during the treatments will be excluded from the analyses,

All randomised patients taking any dose of the trial medication will be included in the safety evaluation (Treated Set).

The handling of randomised patients who received the wrong treatment will be specified in the Trial Statistical Analysis Plan (TSAP).

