6.3 PATIENT SETS ANALYSED

The following nested patient sets are defined:

- Randomised set (RS):

This patient set includes all patients who signed informed consent form and were also randomised, regardless whether the patient was treated with study medication or not.

- Treated set (TS):

This patient set is nested within RS and includes all patients who were dispensed study medication and were documented to have taken any dose of study medication. TS will be used for patient disposition, demographics and baseline disease characteristics, concomitant therapies, treatment compliance, treatment exposure and safety analyses (including AEs and vital signs).

- Full analysis set (FAS):

This patient set is nested within TS and includes patients who had baseline measurement and at least one post-baseline measurement for the primary endpoint or secondary endpoints. Assignment to the FAS will be done after implementation of any data handling rules which set measurements to missing.

- Full analysis set excluding exacerbation (FAS-EE):

This patient set is nested within FAS and the data from patients who have had an exacerbation during the treatments will be excluded from this data set. FAS-EE will be used for the efficacy analyses.

- Per protocol set (PPS):

This patient set is nested within FAS-EE and includes only patients who had no important PVs which are specified to be excluded from the PPS (Table 6.3: 1).

The final decision regarding which patients are excluded from PPS will be made at BRPM or data base lock meeting (DBLM) prior to data unblinding.

Table 6.3: 1 Patient sets analysed

		Patient Sets
Class of endpoint	TS	FAS-EE
Primary endpoint		primary analysis
Secondary endpoints		X
Safety endpoints	X	
Demographic/baseline endpoints/exposure	X	

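### The 80% power in Protocol Section 7.7 belongs to 74 patients evaluable in both periods, but 74 is the number randomised and no loss is allowed for

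*Protocol*

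**What the plan says.** Protocol Section 7.7 states that "a sample size of approximately 74 patients would have 80% to 90% power to reject the null hypothesis" for true differences of 2.5 to 3.0 mL/m². It adds that power would remain 80% at 3.0 mL/m² if the SD were 9.0, and concludes "This results in a sample size of 74 patients". Table 7.7:1 lists 74 in two rows, both at 80% power: 3.0/9.0 and 2.5/7.5.

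The same figure is the recruitment target. Section 7.6 says "Approximately 74 patients will be randomised in blocks to double-blind treatment sequence", Section 3.3 plans for "approximately 74 patients of either sex, 40 to 75 years old, with a diagnosis of COPD are randomised into the study", and the synopsis gives about 74 as the number entered. I found no allowance for loss after randomisation and no rule for replacing patients. The only loss rate given is about 1% withdrawing during screening (Section 2.3), which falls before randomisation.

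On the analysis side, Protocol Section 7.3 says "The data from patients who have had an exacerbation during the treatments will be excluded from the analyses". SAP Section 6.3 turns this into the set FAS-EE and says "FAS-EE will be used for the efficacy analyses"; SAP Section 7.4 names it for the primary analysis. SAP Section 6.6 rules out imputing CMR data. The premature-discontinuation procedures in Protocol Section 6.2.3 list plethysmography and spirometry but no CMR.

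On the SD, Section 7.7 reports the cited cross-over study's mean difference of 3.63 mL/m² "with a standard deviation of approximately 7.3 mL/m"², and then assumes "a within-patient standard deviation of 7.5 mL"/m².

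**The concern.** In a two-period cross-over, the treatment contrast comes almost entirely from patients measured under both treatments. If the calculated N is the number of such patients, it equals the number randomised only when nobody is lost. This plan foresees losses and builds one in: a patient with an exacerbation is randomised and treated, but that patient's data are then removed from the primary analysis. A patient who stops early has no scan scheduled at discontinuation, and the missing value is not filled in.

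What is at stake is whether the stated power describes the analysis that will be run. The two rows that fix N at 74 have almost no margin. One of them carries the protocol's assurance that power survives a 20% larger SD, so a reader would take that assurance as firmer than it is.

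**Working it through.** **Inputs.** Two-sided alpha 0.05; differences 2.5 and 3.0 mL/m²; SDs 7.5 and 9.0 mL/m² (Protocol 7.7); two sequences allocated 1:1 (Protocol 4.1.4.1); about 74 randomised (Protocol 3.3, 7.6). Loss after randomisation: not given.

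**Formula.** For N patients with both periods observed and SD the SD of the within-patient treatment difference, the test has N − 2 degrees of freedom and noncentrality (difference/SD) × √N. Power is the probability that a noncentral t variable exceeds the two-sided 5% critical value. Using N − 1 degrees of freedom changes power by less than 0.1 point.

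**Reproducing Table 7.7:1.** The smallest N, rounded up to an even number for two equal sequences:

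| Difference / SD | Power | Smallest N | Even N | Protocol |
|---|---|---|---|---|
| 3.0 / 7.5 | 80% | 52 | 52 | 52 |
| 3.0 / 7.5 | 90% | 68 | 68 | 68 |
| 3.0 / 9.0 | 80% | 73 | 74 | 74 |
| 3.0 / 9.0 | 90% | 97 | 98 | 98 |
| 2.5 / 7.5 | 80% | 73 | 74 | 74 |
| 2.5 / 7.5 | 90% | 97 | 98 | 98 |

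All six rows match. The table is therefore right, with N as complete pairs and SD as the SD of the paired difference.

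**Power when pairs are lost.** The ratios 2.5/7.5 and 3.0/9.0 are both 1/3, so these two rows always have the same power. With 74 pairs the noncentrality is √74/3 = 2.867 and the critical value (72 df) is 1.993, giving 80.8%. Assumed losses of 5%, 10% and 20% of 74 leave 70, 67 and 59 pairs.

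| Pairs | 2.5/7.5 and 3.0/9.0 | 3.0/7.5 | Difference detectable at 80% power, SD 7.5 |
|---|---|---|---|
| 74 | 80.8% | 92.4% | 2.48 |
| 73 | 80.2% | 92.1% | 2.49 |
| 72 | 79.7% | 91.7% | 2.51 |
| 71 | 79.1% | 91.4% | 2.53 |
| 70 (5% loss) | 78.5% | 91.0% | 2.55 |
| 67 (10% loss) | 76.7% | 89.7% | 2.61 |
| 59 (20% loss) | 71.1% | 85.6% | 2.78 |

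At the whole-percent precision used in Section 7.7, 72 pairs still round to 80% and 71 do not. So the third lost pair takes these two rows below the stated figure. The 3.0/7.5 scenario keeps at least 90% down to 68 pairs (90.1%) and at least 80% down to 52 (80.7%).

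**Slack in the SD.** Section 7.7 rounds the source value of 7.3 up to 7.5. At 2.5/7.3, power is 80.6% with 70 pairs, 80.1% with 69 and 79.5% with 68. If 7.3 is the true SD of the difference, the 2.5 scenario keeps 80% down to 69 pairs.

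**Patients with one period only.** The mixed model keeps them, but they inform the treatment contrast only between patients. If m such patients are all observed in period 1 and split evenly over the sequences, they give a contrast with variance 4σ²/m. The n pairs give 2σ²(1 − ρ)/n, where ρ is the between-period correlation. The singles are therefore worth m(1 − ρ)/2 extra pairs. With ρ assumed between 0.9 and 0.5:

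- 70 pairs + 4 singles: 70.2 to 71.0 effective pairs, power 78.6% to 79.1%.
- 67 pairs + 7 singles: 67.4 to 68.8 effective pairs, power 76.9% to 77.8%.
- 59 pairs + 15 singles: 59.8 to 62.8 effective pairs, power 71.7% to 73.8%.

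This is the favourable case, in which every lost pair leaves a usable single. A patient whose data are all removed under FAS-EE adds nothing.

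**The case against.** The strongest reply has four parts.

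- **There is no arithmetic error, and the trial is exploratory.** The table follows from its inputs, the number is always described as approximate, and the 95% confidence interval to be reported (Protocol 7.3.1) will show the precision achieved. This stands, and it keeps the point to one of wording. Even so, Section 7.2 sets a two-sided 5% test and Section 7.7 gives specific power figures, so they should describe the planned analysis.
- **The size of the shortfall is assumed.** This also stands. The documents give no loss rate after randomisation, and one or two lost pairs change nothing at whole-percent precision.
- **The plan limits losses and has slack.** Exclusion criterion 4 removes patients with a recent exacerbation, scans can be postponed by up to 14 days after oral steroids or theophylline (Section 4.2.1), and visits can be rescheduled (Section 6.1). The step from 7.3 to 7.5 absorbs up to five pairs at 2.5. All of this is fair. But a postponed scan in a patient with an exacerbation is still excluded from the primary analysis, and the SD rounding is not presented as a loss allowance and does not cover a 10% to 20% loss.
- **The mixed model retains incomplete patients.** True, but the gain is at most 2.7 points in the cases above (71.1% to 73.8%) and does not restore 80%.

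A reader might also infer from the phrase "a within-patient standard deviation of 7.5 mL"/m² that 7.5 is a per-period SD, so that the SD of the difference would be √2 times larger and the power far lower. The documents do not support that. Section 7.7 attaches the source SD of 7.3 to the mean difference, and the table reproduces only with 7.5 and 9.0 as SDs of the paired difference. Only the label is loose.

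**Conclusion.** The point holds in a limited form. Table 7.7:1 is arithmetically correct for patients evaluable in both periods. The stated 80% does not carry over to 74 randomised patients analysed in FAS-EE, because the plan's own rules remove pairs and nothing was added to cover this. The two rows that set N at 74 fall below 80% from the third lost pair. The drop from 80.8% is about 2 points at an assumed 5% loss, 4 at 10% and 10 at 20%. The 3.0/7.5 scenario is not endangered over this range.

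A reader might infer that the trial is seriously underpowered or that enrolment must rise. The documents do not support either conclusion: they give no loss rate from which to derive an inflated number, the trial is exploratory, and the shortfall is modest under every loss rate tried here. The figures rest on the protocol's SDs being SDs of the paired difference and on the assumed loss rates. They also treat complete pairs as a close guide to the power of the mixed model.

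**What to change.** In Protocol Section 7.7, or in the SAP:

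1. State that N in Table 7.7:1 is the number of patients with evaluable CMR in both periods after the FAS-EE exclusion, and that no allowance for loss was made.
2. Restate the power for the expected number of such patients, using the sponsor's own blinded or historical loss rate, or a range labelled as an assumption. Possible wording:

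> If 5% to 20% of the 74 randomised patients are not evaluable in both periods (assumption), 70 to 59 pairs remain. Power is then about 79% to 71% at 2.5/7.5 and at 3.0/9.0, and about 91% to 86% at 3.0/7.5. The difference detectable with 80% power at an SD of 7.5 is 2.55 to 2.78 mL/m², compared with 2.48 mL/m² for 74 pairs.

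3. Relabel 7.5 and 9.0 as the SD of the within-patient treatment difference, which is how the table uses them. This is a clarification of wording only.

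The cost is a few sentences and a slightly less favourable power statement. Patient numbers and the analysis stay as they are.
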